2.2 SCHEMA

2.3 SCHEDULE OF ACTIVITIES (SOA)

	Study ETT Placement	ICU Day 1	ICU Day 2 to Extubation	ICU Discharge	Hospital Discharge	VAE Event ¹	Extubation	6-month Follow-up
Randomization assignment	X							
Daily screening for new mechanical ventilation or study ETT use	X							
Enrollment		X						
Pregnancy test ²		X						
Informed consent		X						
Study ID number assignment		X						
Intubation location/details		X						
Baseline characteristics								
Demographics ³		X						
ICU location		X						
Admission diagnosis		X						
Indication for MV		X						
CAP at admission ⁴		X						
Charlson (history only) ⁵		X						
Charlson (admit or history) ⁶		X						
APACHE II		X						
Daily VAE/VAP surveillance								
FiO ₂		X	X			X		
PEEP		X	X			X		
Temperature		X	X			X		
WBC		X	X			X		
Secretion quantity and quality		X	X			X		
Respiratory cultures		X	X			X		
Respiratory antimicrobials ⁷		X	X			X		
CXR interpretation ⁸		X	X			X		
VAP preventive measures								
Stress-ulcer prophylaxis		X	X					
Use of probiotics		X	X					
Enteral nutrition		X	X					
Oral chlorhexidine care		X	X					
Head of bed elevation >30°		X	X					
ETT cuff pressure compliance		X	X					
Daily sedation vacation		X	X					
Daily SBT		X	X					
Subglottic suction compliance		X	X					
Airway characteristics								
Cuff leak prior to extubation		X	X				X	
Post-extubation complications ⁹				X	X		X	
Laryngeal/speech evaluation ¹⁰								X
Device-related adverse event		X	X	X	X		X	X
Serious adverse event		X	X	X	X		X	X
ICU characteristics								
Mechanical ventilation duration		X	X				X	
Reintubation ¹¹				X	X		X	
Tracheostomy				X	X			
Surgical procedure				X	X			
PaO ₂ /FiO ₂ ratio		X	X			X		

Daily SOFA		X	X	X			X	
Selected concomitant medications ¹²		X	X	X			X	
Discharge disposition					X			
Quality of Life (Short Form-36)								X
Cognitive Function (NACC UDS)								X
Vital status				X	X			X
Cause of death				X	X			X

Abbreviations: ICU: intensive care unit; ETT: Endotracheal tube; MV: Mechanical Ventilation; CAP: Community-acquired pneumonia; VAE: Ventilator associated events; VAP: Ventilator-associated pneumonia; APACHE II - Acute Physiology, Age, Chronic Health Evaluation II; WBC: white blood count; CXR: chest x-ray; SBT: spontaneous breathing trial; SOFA - Sequential Organ Failure Assessment; NACC UDS: National Alzheimer's Coordinating Center Uniform Data Set.

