The primary analysis described above provides valid inference if the missing response data is missing at random (MAR). However, in the case that the data are not missing at random (NMAR), the results of the proposed analyses may be biased. We will perform sensitivity analyses to assess the impact of the missing outcome data. We will employ standard multiple imputation methods to assess the degree to which the primary analysis may be affected by the missing data. Patient retention will be key to the successful completion of this study, and we will take several measures to maximize retention. We expect missing data due to “losses to follow up” to be minimized by our efforts. We will make every reasonable effort to retain the patients through follow-up to preserve the integrity of the study and to minimize

possible bias associated with loss due to dropouts. We realize that these investigations of missing data or accruing additional patients to meet targeted sample sizes are not foolproof substitutes to remedy missing data.⁸ We intend to make every reasonable attempt to maximize the rate of follow up in our sampled population. We will minimize the loss of follow-up data by continuing to have clear performance standards in the protocols to achieve high quality trial conduct, including high levels of data capture. We will continue to monitor and carefully educate providers as well as patients or their representatives during the informed consent process regarding the scientific relevance, and we will also monitor data collection to ensure quality standards are met, including targeted levels of data capture.

Changes to the Statistical Analysis Plan

Changes to this statistical analysis plan will be documented via a formal addendum that includes rationale, new procedures, and potential differences from prior plan.

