Specifically, we will evaluate whether there is a difference in the laryngeal injury risk probabilities for the two treatments, we will use maximum likelihood estimation (binomial family) with an identity link function. The statistical model used for this analysis will be: $p(X) = \beta_0 + \beta_1 X$ where $p(X)$ denotes the laryngeal injury probability and X is an indicator denoting the treatment assignment (1 = EVAC-PU-ETT, 0 = PVC-ETT). The identity link function makes the interpretation of parameter for the treatment effect, β_1 , be equal to $\beta_1 = p(1) - p(0)$, which is exactly the risk difference, q , noted above. In the Prevent pilot study, the estimated risk of laryngeal injury was 0.39 for the PVC-ETT treatment group and 0.38 for the EVAC-PU-ETT treatment group. Assuming an estimated risk difference less than or equal to 0.05 for the targeted sample size of $N=1074$ (537 patients per treatment arm) for the pre-specified alpha-level and statistical design, the statistical power for concluding non-inferiority of the EVAC-PU-ETT treatment group would be 80 percent.

Analysis of Quality of Life Primary Endpoint

We will evaluate whether there are differences in quality of life measures between treatment groups by comparing mean scores. Separate analyses will be conducted for the two endpoints. The statistical model will be linear regression, $\mu(X) = \beta_0 + \beta_1 X$, where $\mu(X)$ denotes the mean SF-36 score, X is an indicator denoting the treatment assignment as before. The test for a treatment effect is denoted by, $\beta_1 = \mu(1) - \mu(0)$. We will use robust inference so that our tests will be valid for modest departures in modeling assumption. Additionally, we will transform the scores to reflect “percent of healthy life”. This transformation of the SF-36 measures provides easily interpretable variables and allow for the retention of patients that die during the study. As noted previously, the design for this endpoint is a fixed sample design. To have power of at least 80 percent for the targeted sample size of $N=1074$, we require a difference in the means to be greater than 0.17 standard deviations on a standardized scale. These

power and effect size calculations assume an independent, two-sample test, an alpha level of five percent and all statistical tests are two-sided tests.

Analysis of Cognitive Impairment Primary Endpoint

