To evaluate whether there is a difference in the risk of cognitive impairment between the two treatments, we will use the same fixed sample methods used for the primary safety endpoint. We will estimate the difference in the probability of cognitive impairment for the two treatments using maximum likelihood estimation (binomial family) with an identity link. We will use robust (sandwich) standard error estimates in the test statistics and confidence intervals to remedy possible minor violations of modeling assumptions. The design for this endpoint is a fixed sample design. We assumed a prevalence of cognitive impairment of 0.40 for this at population, a sample size of N=1074, we require a minimum risk difference of 0.09 ($q = p_1 - p_0 < -0.09$) to attain statistical power of at least 80 percent. We assumed a prevalence of cognitive impairment of 0.40, however, the risk difference of 0.09 attains the targeted level of power or higher, for a prevalence in a reasonable range (e.g., 0.2-0.8).

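### The statement that the primary QoL and cognition analyses are valid under MAR needs a condition: the arm-only models are valid only if missingness is unrelated to outcome given arm

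*Combined protocol and SAP*

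**What the plan says.** Under Missing Data in section 10.2, the primary analysis "provides valid inference if the missing response data is missing at random". No conditioning variables are named. The next sentence limits the concern: "in the case that the data are not missing at random (NMAR), the results of the proposed analyses may be biased". The remedy offered is a sensitivity analysis: "We will employ standard multiple imputation methods to assess the degree to which the primary analysis may be affected by the missing data". The variables that would enter the imputation are not listed.

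Section 10.4.2 gives the primary models. For SF-36, "The statistical model will be linear regression", and "X is an indicator denoting the treatment assignment as before". Cognitive impairment is compared "using maximum likelihood estimation (binomial family) with an identity link", again as a two-arm contrast. Neither model has a covariate, a weight or a repeated measure. For SF-36, section 10.4.2 adds a transformation of the scores that lets patients who die be kept in. It gives no counterpart for cognition.

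The Schedule of Activities (2.3) places both outcomes at the 6-month visit only, and section 4 notes that no neuropsychological tests from before the illness will be available. Sections 2.3 and 9.1 show that the hospital course is recorded in detail: VAE surveillance, ventilation duration, tracheostomy, daily SOFA, lengths of stay and discharge disposition.

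**The concern.** The documents never use the term complete-case. It is implied, because section 10.4.2 names no handling of missing outcomes and section 10.2 keeps imputation for sensitivity. An outcome measured once and regressed on arm alone draws only on patients seen and conditions on nothing but arm. MAR is wider: it lets attendance depend on anything recorded, including the hospital course. So the data can be MAR while the fitted difference is biased, and section 10.2 gives the reader no warning of that.

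This matters here because sections 3.3.1 and 10.1 hypothesise that the tube works by preventing VAP, which means changing the hospital course. If patients with a bad course attend less often, the analysis under-represents those who carry the effect. If such patients attend at different rates in the two arms, a difference can appear where none exists. Poorer attendance by sicker survivors at a 60 to 75 minute in-person visit (9.1) is plausible, and bedside care is not blinded (5.1).

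**Working it through.** **1. The plan's own figures, for scale.** With 537 per arm and two-sided 5%:
- QoL, 0.17 SD: Φ(0.17 × √(537/2) − 1.96) = Φ(0.826) = 0.795, against the stated 80%.
- Cognition, 0.40 vs 0.31, pooled variance under the null: Φ((0.09 − 1.96 × 0.0292)/0.0291) = 0.870, against at least 80%.

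Both agree with section 10.2. Neither allows for missing outcomes, and the documents state no expected attendance.

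**2. What the arm-only fit estimates.** Let X be arm, U a recorded bad hospital course, R attendance and Y the outcome. If R depends only on X and U, the data are MAR given X and U. The mean among attenders in arm x is Σ P(U=u | R=1, X=x) × E[Y | X=x, U=u]. The target uses P(U=u | X=x) as weights. The two agree if attendance depends on arm alone, and in general differ otherwise.

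**3. Closed form.** Let v be the share with U in an arm, aB and aG the attendance with and without U, and iB and iG the corresponding outcome means. The share with U among attenders is v′ = v·aB / (v·aB + (1−v)·aG). If U acts on Y equally in both arms, and the device acts only through U:
- full-data difference = (v_EVAC − v_PVC)(iB − iG)
- observed difference = (v′_EVAC − v′_PVC)(iB − iG)

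The 8% vs 22% is the VAP result of the randomized trial of a PU-cuffed tube with subglottic aspiration, cited in section 3.2. **All attendance and outcome rates are assumptions.**

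Worked example, aB = 0.50, aG = 0.80:
- v′_PVC = 0.110/0.734 = 0.150
- v′_EVAC = 0.040/0.776 = 0.052
- Gap among attenders −0.098 against −0.140 in full, a ratio of 0.70, so 30% is lost whatever iB and iG are.

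| Case | U, EVAC / PVC | Attendance with / without U | Outcome with / without U | Full | Observed |
|---|---|---|---|---|---|
| A. Arm only | 8% / 22% | 90% EVAC, 70% PVC, regardless of U | cognition 0.60 / 0.35 | −0.035 | −0.035 |
| B. Course balanced, same pattern | 22% / 22% | 50% / 85% | cognition 0.60 / 0.35 | 0 | 0 |
| C1. Device changes course | 8% / 22% | 50% / 80% | cognition 0.90 / 0.26 | −0.090 | −0.063 |
| C2 | 8% / 22% | 40% / 85% | cognition 0.90 / 0.26 | −0.090 | −0.050 |
| C3 | 8% / 22% | 50% / 80% | cognition 0.70 / 0.32 | −0.053 | −0.037 |
| C4 | 8% / 22% | 65% / 80% | cognition 0.70 / 0.32 | −0.053 | −0.046 |
| C5 | 8% / 22% | 50% / 85% | QoL 1.0 SD lower with U | 0.140 SD | 0.094 SD |
| D1. Pattern differs by arm | 22% / 22% | EVAC 80% / 85%, PVC 50% / 85% | QoL 1.0 SD lower with U | 0 | −0.067 SD |
| D2 | 22% / 22% | as D1 | cognition 0.60 / 0.35 | 0 | +0.017 |

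Swapping the arms in D reverses the signs.

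**4. Power in C1.** About 394 PVC and 417 EVAC patients are seen (537 × 0.734 and 537 × 0.776). Approximate power is Φ(0.0629/0.0328 − 1.96) = 0.48. With the same numbers seen and no bias it is Φ(0.0896/0.0335 − 1.96) = 0.76.

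**5. Simulation.** 4,000 trials of 1,074 patients per scenario, a recorded severity score correlated −0.5 with QoL, and about 75% attendance. With no true effect:
- Same log-odds slope of attendance on severity in both arms (0.8): type I error 0.053.
- Slopes 0.8 (PVC) vs 0.4 (EVAC): QoL bias about −0.046 SD, type I error about 0.10.
- Slopes 0.8 vs 0: about −0.09 SD, type I error about 0.27.

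With equal slopes and a device effect on severity (true QoL effect 0.171 SD), the arm-only fit gave 0.156. Regression standardisation on severity within arm recovered the truth to rounding in each of these scenarios. It stands in here for imputation on the same variable.

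**The case against.** **MAR depends on the conditioning set.** If the only data considered are outcome and arm, MAR means that missingness depends on arm alone, and the sentence is then correct. This stands as a technical reading, so a reader should not infer that the sentence is false in every sense. But the plan states it without qualification in a trial that records the hospital course in detail.

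**Bias is not automatic.** A reader might infer that any dependence of attendance on the hospital course biases the primary results or inflates false positives. The documents do not support that. In case B the bias is exactly zero, and with no effect and equal patterns type I error stays near 5%.

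**Multiple imputation is already planned.** True, and it could correct this bias. But it is only a sensitivity analysis and no variables are named; imputing from arm alone would reproduce the same bias.

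**Retention is taken seriously.** Home visits, compensation, multiple contacts and tracing (6.4, 8.3) target the patients assumed here to attend poorly, and section 10.2 admits that its remedies are not foolproof. This may make the problem small; it does not make the sentence right.

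**The illustrations may be generous.** Impairment of 0.90 with VAP was chosen so that the planned 0.09 runs wholly through VAP. Section 3.2 also cites a 604-patient trial in which cuff shape and material did not affect VAP rates, and section 5.1 expects many extubations within 48 hours, so 22% may be high. In C3 the bias is 0.016, about half a standard error; in C4 it is about 0.2. All of this stands as to size.

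**Conclusion.** The validity statement in section 10.2 is incomplete for the QoL and cognition models. An observed-outcome fit with arm alone is valid only when missingness is unrelated to outcome given arm. Under MAR given the recorded hospital course it can be biased by two routes: the device changes the course, as the trial hypothesises, or attendance depends on the course differently by arm. Neither route requires data that are not missing at random.

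Size and direction cannot be fixed from the documents, which give no attendance rate. Under the assumptions above, the first route loses about 14% (C4) to 44% (C2) of the cognition effect, with 30% at attendance of 50% and 80%. The QoL illustration (C5) loses about one third. The second route gives up to about 0.02 in cognition risk or 0.07 SD in QoL in the closed-form cases, with either sign. These figures show that the bias is possible; they do not predict it.

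**What to change.** - **Section 10.2:** state that the treatment-only models are valid only when missingness is unrelated to outcome given arm.
- **Imputation:** specify the multiple imputation already planned. Apply it to survivors without a 6-month assessment, separately by arm, using baseline variables and the hospital course already collected (VAE/IVAC status, ventilation days, tracheostomy, SOFA, ICU and hospital stay, discharge disposition). Follow it with the same linear and identity-link models. For patients who withdraw, use data up to withdrawal, since collection then stops (11.1.1.2).
- **Status:** preferably make this the primary analysis of QoL and cognition in section 10.4.2, with the observed-outcome fit as sensitivity.
- **Deaths:** keep them outside the imputation, handle them for QoL through the transformation in section 10.4.2, and state that the cognition comparison is among survivors.

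The cost is SAP wording, through the addendum route that section 10.2 provides, and some extra analysis. No new data are needed. The downside is that the result then depends on a stated imputation model.

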8.3 LOST TO FOLLOW-UP

Obtaining complete data is a high priority for this trial because missing data could compromise the validity of the entire study. A participant will be considered lost to follow-up if he or she fails to return for the 6-month follow-up visit and is unable to be contacted by the study site staff.

The following actions must be taken if a participant fails to appear for the 6-month follow-up visit:

- The site will attempt to contact the participant and reschedule the missed visit and counsel the participant on the importance of maintaining the assigned visit schedule and ascertain if the participant wishes to and/or should continue in the study.
- Before a participant is deemed lost to follow-up, the investigator or designee will make every effort to regain contact with the participant. These contact attempts should be documented in the participant's study file.
- Should the participant continue to be unreachable after several attempts, he or she will be considered to have withdrawn from the study with a primary reason of lost to follow-up.

We will capture deaths among participants lost to follow up using various mechanisms, including review of the medical record, contacting the legal next of kin, or the contact provided at the time of study enrollment. For patients who are lost to follow up, we will also contact the primary care physicians and safety net clinics to ascertain the participant's vital status. In addition, local obituaries and newspapers will be screened for potential identification of lost to follow-up study participants.

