10.4.5 BASELINE DESCRIPTIVE STATISTICS

For the baseline descriptive statistics, we will present overall sample summary characteristics, e.g., mean, standard deviations, and percentages. We will also provide summaries of the baseline characteristics stratified by treatment assignment to describe the patient population and to evaluate the balance in the randomization assignment. We will also provide information on data completeness and retention to follow up.

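### The plan warns that outcomes not missing at random could bias the quality-of-life and cognition results but specifies no analysis of that departure; prognostic baseline data are also left out of both primary models, at a cost in precision only

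*Combined protocol and SAP*

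**What the plan says.** **Missing data.** The Missing Data text in section 10.2 says the primary analysis is valid under MAR, and then that "in the case that the data are not missing at random (NMAR), the results of the proposed analyses may be biased". It promises sensitivity analyses in general terms and names one method: "We will employ standard multiple imputation methods to assess the degree to which the primary analysis may be affected by the missing data". It does not list the imputation variables or any parameter for departure from MAR. Section 8.3 rates the threat highly: "missing data could compromise the validity of the entire study".

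**Primary models.** In section 10.4.2 the quality-of-life regression has one predictor, X, which "is an indicator denoting the treatment assignment as before". The cognition analysis reuses the method of the safety endpoint, whose model also contains treatment alone. It estimates the "difference in the probability of cognitive impairment for the two treatments using maximum likelihood estimation (binomial family) with an identity link". No covariate is named for either.

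**Deaths.** For quality of life, an additional percent-of-healthy-life transformation is meant to "allow for the retention of patients that die during the study". It does not deal with survivors who are not seen.

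**Baseline data.** Sections 2.3 and 9.1 schedule demographics, two Charlson lists, APACHE II and intubation location. Section 5.1 describes two enrolling hospitals. Section 10.4.5 uses baseline data only "to describe the patient population and to evaluate the balance in the randomization assignment".

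**The concern.** Both outcomes need a 6-month in-person visit, which section 9.1 puts at 60 to 75 minutes. Survivors too ill or too impaired to attend may differ from those seen in ways the recorded data do not explain. That is the NMAR case the plan itself raises. An imputation that assumes MAR sets the departure to zero, so agreement with the primary analysis says nothing about it. A significant result could rest on unseen survivors, and the plan gives no way to show how different they would have to be.

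The second part is smaller. Prognostic information known before the tube was placed is collected but not used to reduce the variance of the primary contrasts.

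**Working it through.** **Inputs from section 10.2:** 537 per arm; two-sided 5%; quality-of-life difference 0.17 SD (example SDs 30 for MCS and 40 for PCS); cognitive impairment 0.40, risk difference 0.09, so 0.40 against 0.31. **Assumed:** fraction of survivors followed (f), mortality (d), R² and departure from MAR (delta). The documents give none of these. Section 3.2 quotes mortality for patients with VAP, not for all intubated patients.

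**1. The plan's power.** Quality of life: Φ(0.17·√(537/2) − 1.96) = 0.795, against 80% stated. Cognition: SE = √[(0.40·0.60 + 0.31·0.69)/537] = 0.0291, and Φ(0.09/0.0291 − 1.96) = 0.872, consistent with at least 80%. The stated figures reproduce.

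**2. Can MAR imputation reveal an NMAR problem?** In a simulation with no true difference, missing EVAC-PU-ETT patients were set 0.5 SD worse than those observed. Imputation was within arm, without covariates (10 imputations, 1,500 replicates).

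| Missing | Bias, observed cases | Bias, MAR imputation | Rejection rate, MAR imputation |
|---|---|---|---|
| 10% | 0.05 SD | 0.05 SD | about 13% |
| 20% | 0.10 SD | 0.10 SD | about 31% |
| 30% | 0.15 SD | 0.15 SD | about 53% |

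The imputed analysis repeats the primary one. Adding covariates makes MAR more plausible but does not test departure from it.

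**3. Tipping points.** These take the observed effect at the target and let missing EVAC-PU-ETT survivors alone be worse than MAR predicts. The number observed per arm is n = 537·(1−d)·f.

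- Quality of life: delta = (0.17 − 1.96·√(2/n))/(1−f). With f = 0.80 and d = 0, n = 429.6, SE = 0.0682, and delta = (0.17 − 0.1337)/0.20 = 0.18. With d = 0.20, n = 343.7, SE = 0.0763, and delta = (0.17 − 0.1495)/0.20 = 0.10.
- Cognition: solve 0.40 − p = 1.96·√[(0.40·0.60 + p(1−p))/n] with p = 0.31 + (1−f)·t, where t is the extra impairment risk. With f = 0.80 and d = 0, p = 0.3357 and t = 0.0257/0.20 = 0.128.

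| Survivors followed | Mortality | Quality of life (SD) | Cognition (percentage points) |
|---|---|---|---|
| 90% | 0 | 0.44 | 29 |
| 80% | 0 | 0.18 | 13 |
| 80% | 20% | 0.10 | 9 |
| 80% | 30% | 0.05 | 7 |

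On the plan's SDs, 0.18 SD is about 5 MCS points (0.181·30 = 5.4) or 7 PCS points (0.181·40 = 7.2). Simulated imputation with Rubin's rules agrees for the no-death rows: mean z falls from 2.64 to 1.95 at 90% followed with delta 0.439, and from 2.48 to 1.96 at 80% with delta 0.181.

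**4. Which departures count.** The shift is m_E·delta_E − m_P·delta_P, where m is the missing fraction in each arm. With equal fractions, equal deltas cancel. With 10% against 20% missing, a common delta of 0.25 to 0.5 SD shifts the difference by 0.10·0.25 = 0.025 to 0.10·0.5 = 0.05 SD.

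**5. Precision.** Quality-of-life power at 0.17 SD is Φ(0.17·√(537f/(2(1−R²))) − 1.96).

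| Followed (no deaths) | R² = 0 | R² = 0.05 | R² = 0.30 |
|---|---|---|---|
| 100% | 79.5% | 81.5% | 91.5% |
| 90% | 75.3% | 77.4% | 88.5% |
| 80% | 70.2% | 72.5% | 84.6% |

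There is no baseline SF-36 in section 2.3, so the low end, about 2 points, is likelier. For cognition with complete data, assumed covariate AUCs of 0.57 to 0.69 move power from 87.2% to between 87.6% and 90.5%. That gain is small, partly because section 4 already norms the tests for age, sex and education.

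**The case against.** **The plan does not rule NMAR out.** A reader might infer that section 10.2 restricts itself to a MAR imputation. It does not say so: the imputation is never labelled MAR, sensitivity analyses are promised in general, and the text concedes that such investigations cannot fully repair missing data. Delta-adjusted imputation is itself a form of multiple imputation. This stands, and the point is therefore only that no NMAR analysis is specified. A method chosen after the data are seen would not fill that gap convincingly.

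**The tipping points are chosen cases.** They assume an effect exactly at target and departure in one arm. An observed 0.25 SD at 80% followed with no deaths would need (0.25 − 0.1337)/0.20 = 0.58 SD. Section 7.3 says primary outcomes are determined without knowledge of device, and no section suggests that unseen survivors differ by arm. This also stands: the figures show what the plan could not detect, and do not predict bias.

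**Unadjusted analysis is valid.** With complete data it is, by randomisation. A reader might infer that treatment-only models are biased even under MAR. That would need severity-dependent loss that differs between arms, and nothing in the documents indicates it. Changing a primary model for perhaps 2 points of power is a matter of judgement, and 90 patients have already completed follow-up.

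**Conclusion.** The concern holds in a limited form. The plan names NMAR as a source of bias and specifies no analysis of it. The one method named, on its ordinary reading, carries the MAR assumption forward. That absence is clear from the text.

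The size is conditional. Every follow-up rate, mortality, R² and delta above is assumed. The no-death tipping points overstate the tolerance of a survivors-only analysis, where at 80% followed it falls to 0.10 or 0.05 SD and 9 or 7 points. The quality-of-life figures do not carry over to the percent-of-healthy-life scale, which changes both the mean and the SD.

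The missing covariates are an inefficiency, not an error, and are the lesser half of the point. How deaths enter the cognition analysis is a separate question.

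**What to change.** **1. Missing data.** Keep multiple imputation and state its model: by arm, for survivors without a 6-month score, from the baseline covariates plus in-hospital severity and course (APACHE II, SOFA, IVAC, length of stay, discharge disposition). Add a delta-adjusted (tipping-point) analysis for quality of life and cognition, with delta varied separately by arm. Do not impute outcomes for patients who died.

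**2. Covariates.** Pre-specify a short list fixed before intubation: age, chronic comorbidities from both Charlson lists, hospital, and ED against in-hospital intubation. Footnote 5 of section 2.3 alone would omit dementia, diabetes, and respiratory and renal disease, which are in footnote 6. Count only conditions that pre-date intubation, including pre-existing dementia. Put these covariates in the primary quality-of-life models. For cognition, report a standardised risk difference from a logistic model with robust standard errors. Keep the unadjusted results as supportive. APACHE II is scheduled on ICU Day 1, after tube placement, and insertion events such as desaturation could affect it. Keep it out of the primary model unless it is scored from earlier values.

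Leave the group-sequential safety test in section 10.4.2 unchanged.

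**Cost.** SAP wording and modest programming, through the addendum route section 10.2 already provides and before outcomes are examined by arm. No new data are needed.
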